2.5.4 Supportive analyses

A sensitivity analysis will be conducted for PPS if there is a more than 10% difference between the FAS and PPS samples.

2.6 Analysis of the key secondary objective

There is no key secondary objective for this study.

2.7 Analysis of secondary efficacy objective(s)

2.7.1 Secondary endpoints

The following secondary outcome measures will be analyzed:

- 1. The proportion of patients who tolerate the LCZ696 dose of 97 mg sacubitril / 103 mg valsartan mg bid at 12 months of treatment.
- 2. The proportion of patients on LCZ696 who had required down-titration after reaching the 97 mg sacubitril / 103 mg valsartan
- 3. The number of down-titration changes from 97 mg sacubitril / 103 mg valsartan during 12 months of treatment.
- 4. Functional capacity as measured by the change from baseline to 6 months and 12 months in the Six Minute Walk Test.
- 5. Time to each up-titration to 49 mg sacubitril / 51 mg valsartan and 97 mg sacubitril / 103 mg valsartan.
- 6. Duration of treatment on each dose of LCZ696.
- 7. The proportion of patients on guideline-recommended doses and who are tolerant of beta-blockers and MRAs at baseline, 6 and 12 months.

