PARADIGM-HF was a phase III randomized controlled trial conducted in HFrEF patients that were well controlled on background therapy including ACEIs/ARBs,  $\beta$ -blockers and MRAs. The results of this study showed that, when compared to enalapril, LCZ696 significantly reduced the risk of the composite endpoint of CV death or HF hospitalization by 20% after 27 months (8). In the same study LCZ696 also reduced the risk of all-cause mortality by 16%, and the number of all-cause hospitalizations, CV and HF hospitalizations (including first and recurrent hospitalizations). LCZ696 was also found to be safe well tolerated. These results prompted recent changes to the Canadian Cardiovascular Society HF treatment guidelines, according to which LCZ696 has replaced ACEI inhibitors or ARBs in patients with HFrEF.

The TITRATION randomized controlled study enrolled HFrEF patients who were either naïve or already treated with ACEIs or ARBs treated (with  $EF \le 35\%$ ) that were on any dose of ACEIs or ARBs managed as in-patients or outpatients before enrolment (9). The study compared a condensed regimen in which the dose of LCZ696 was up titrated from 24 mg sacubitril / 26 mg valsartan bid to 49 mg sacubitril / 51 mg valsartan bid in 3 weeks to a conservative regimen in which the up-titration was conducted over 6 weeks. The results showed that LCZ696 was well tolerated and the majority of patients were able to achieve the 97 mg sacubitril / 103 mg valsartan bid target dose without any dose adjustment or interruption over 12 weeks regardless of the ACEIs or ARBs used at baseline. Among the 466 randomized patients, excluding those who discontinued due to non-AE related reasons, 77.8% in the condensed regimen and 84.3% in the conservative regimen achieved the target LCZ696 97 mg sacubitril / 103 mg valsartan bid dose and had no down-titration or dose interruption (Senni et al, ESC-HF May 2015). The results of this study show that up-titration of LCZ696 from 24 mg sacubitril / 26 mg valsartan to the optimal 97 mg sacubitril / 103 mg valsartan bid is safe and well tolerated in a wide range of patients with HFrEF.

Generalization of the results of controlled clinical trials to the real-life setting is problematic

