## 5.5.5 Instructions for prescribing and taking study treatment

During the baseline visit all patients will be instructed to stop taking their ACEIs for 36 hours prior to taking the first dose of LCZ696. Patient receiving an ARBs will only have to discontinue their medication and start LCZ696 at the next schedule time. All patients will be initiated on LCZ696 at 24 mg sacubitril / 26 mg valsartan that can be up-titrated to LCZ696 49 mg sacubitril / 51 mg valsartan bid after 2-4 weeks and then up-titrated again to 97 mg sacubitril / 103 mg valsartan bid after another 2 – 4 weeks. Timing of LCZ696 up-titration will be dependent on patient tolerability and the judgement of the physician.

If patients experience any lack of tolerability including but not limited to hypotension and hyperkalemia, the dose of LCZ696 may be reduced or treatment suspended or terminated as per the judgement of the treating physician.

All dosages prescribed and dispensed to the patient and all dose changes during the study must be recorded on the Dosage Administration Record CRF.

The investigator should promote compliance by instructing the patient to take the study treatment exactly as prescribed and by stating that compliance is necessary for the patient's safety and the validity of the study. The patient should be instructed to contact the investigator if he/she is unable for any reason to take the LCZ696 as prescribed.

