# 6.5 **Appropriateness of efficacy assessments**

The outcome measures are in line with the overall study purpose and objectives. More specifically, the proportion of patients achieving and maintaining treatment with 97 mg sacubitril / 103 mg valsartan bid LCZ696 is the outcome for the primary objective. The time to reaching the dose of 97 mg sacubitril / 103 mg valsartan bid for LCZ696 is relevant in understanding how the up-titration algorithm is applied in the real – life setting. The duration on treatment on 24 mg sacubitril /26 mg valsartan and 49 mg sacubitril / 51 mg valsartan bid LCZ696 is complementary information to the understanding of the real – life implementation of the up-titration scheme for LCZ696. The rate of down – titration of LCZ696 is an indication of tolerability. The change in functional capacity as measured by the six minute walk test, is an important outcome given that it will demonstrate that LCZ696 is not only tolerated at 97 mg sacubitril / 103 mg valsartan bid but also effective in reducing the impact of heart failure.

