2.7.2 Statistical hypothesis, model, and method of analysis

The data analysis will be primarily descriptive. For the secondary efficacy outcomes, the proportion of patients on LCZ696 97 mg sacubitril / 103 mg valsartan bid at 12 months, the proportion of patients requiring down titration, and the proportion of patients treated in accordance to guideline recommended doses of beta blockers and MRAs will be presented along with the 95% Confidence Intervals using binomial proportion to assess the precision.

Novartis	For business use only	Page 14
SAP		PARASAIL / LCZ696BCA02

The number of down titrations during the 12 month treatment periods will be described with a Poisson distribution and the incidence density rate (IDR) as the number of dose reductions per 100 person – month of follow up.

The change in the Six Minute Walk Test from baseline to 6 and 12 months of treatment will be assessed along with the 95% confidence intervals using Student's t-test for paired observations.

The time to LCZ696 up-titration to 97 mg sacubitril / 103 mg valsartan bid and the duration on treatment for each dose will be assessed with the Kaplan Meier estimator of the survival function.

Duration of treatment on each dose of LCZ696 will be summarized descriptively.

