5.4.2 Secondary anlysis

For Incidence density rate for the number of dose reduction, following code may be used:

```
<Sample code>
proc genmod data=mydata;
model ndt =/dist=poisson link=log obstats; /* where ndt is the number of down
titrations for each of the patients.*/
```

run;

For Kaplan-Meier estimates of the probability of reaching LCZ 200 mg, following code may be used:

```
ods listing close;
proc lifetest data = <xxx> outsurv = <xxx> ;
    time TIME*censor(0);
    ods output productlimitestimates = res;
    ods output HomTests=pvalue;
    ods output Quartiles=med;
run;
ods listing;
```

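### The down-titration endpoints have no rule for patients who stop or suspend LCZ696 directly from 97/103 mg, so they can understate intolerance of that dose

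*SAP*

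**What the plan says.** SAP 2.7.1 lists two endpoints on loss of the target dose. Item 2 is "The proportion of patients on LCZ696 who had required down-titration after reaching the 97 mg sacubitril / 103 mg valsartan". Item 3 is "The number of down-titration changes from 97 mg sacubitril / 103 mg valsartan during 12 months of treatment". Protocol 6.4.2 and 9.4.1.2 carry the same two measures. SAP 2.7.2 analyses item 3 with a Poisson distribution and "the incidence density rate (IDR) as the number of dose reductions per" 100 person-months of follow-up. The comment in the sample code of SAP 5.4.2 reads "where ndt is the number of down" titrations for each patient. None of these places defines down-titration.

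The protocol keeps the possible actions apart. Section 5.5.5 says that, when a patient does not tolerate treatment, "the dose of LCZ696 may be reduced or treatment suspended or terminated as per the judgement of the treating physician". Section 5.5.6 uses down-titration for a move to the next lower dose level. It treats a complete stop as a separate step, after which the patient should leave the trial.

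On interpretation, Protocol 6.5 states: "The rate of down – titration of LCZ696 is an indication of tolerability".

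**The concern.** Tolerability of 97/103 mg is the subject of the study, and items 2 and 3 are the measures built specifically around losing that dose. If they register only a step to a lower tablet strength, a patient taken straight off the drug contributes nothing to either. Such exits are foreseeable: Protocol 5.5.10 and Appendix 2 contain provisions under which study drug is stopped from whatever dose the patient is on.

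The measure then responds in the wrong direction to practice. For the same number of patients who cannot stay on 97/103 mg, a site that stops outright shows fewer down-titrations than a site that steps down, and the dose looks better tolerated on these two endpoints.

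**Working it through.** **1. Is there a rule that catches direct stops?**
- Items 2 and 3, the rate and the sample code name down-titrations or dose reductions only.
- Protocol 5.5.5 and 5.5.6 use reduction, suspension and termination as different actions, so the narrow reading of down-titration is the natural one.
- SAP 2.7.3 deals only with patients lost to follow-up after reaching 97/103 mg. It classes them as not staying on treatment and does not make them a down-titration event.
- Item 2 refers to patients on the drug. This may keep stoppers in the denominator as non-events or drop them altogether; the SAP does not say which.

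**2. Where do these patients appear instead?**
- Primary endpoint (SAP 2.5.1): the denominator is everyone with at least one dose, so a patient off drug at month 6 counts against the dose. Item 1 shows the same at month 12 if it uses the same denominator.
- Disposition (SAP 2.3.1) gives reasons for discontinuation. SAP 2.8.1 tabulates adverse events causing discontinuation and, in one merged table, those requiring dose adjustment or interruption. None of these is specified by dose level.
- Duration on each dose (item 6) probably ends at a direct stop, but the event and censoring rule is not written down.
- A suspension that ends before month 6 or month 12 is not seen by the proportion-at-target endpoints. In the adverse event tables it shows only if an event was recorded.

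**3. The plan's own figure.** The only stated precision is for the primary proportion: 1.96 × √(0.70 × 0.30 / 300) = 0.052, giving 64.8% to 75.2%, and 0.052 / 0.70 = 7.4%. This reproduces. No figure is given for items 2 or 3.

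**4. Illustration.** Inputs from SAP section 3: N = 300, about 80% reaching 97/103 mg in earlier trials, 70% expected at 6 months. Assume that 0.80 × 300 = 240 reach the dose and 0.70 × 300 = 210 remain, so 240 − 210 = 30 leave it. Assume further that everyone has 12 months of follow-up except stoppers, who have 6. Person-months are then 300 × 12 − 6 × (number of direct stops).

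| Direct stops among the 30 | Step-downs | Step-down only, of 240 | Any move off, of 240 | Person-months | Step-downs per 100 person-months | Combined per 100 person-months |
|---|---|---|---|---|---|---|
| 0 | 30 | 12.5% | 12.5% | 3600 | 0.83 | 0.83 |
| 15 | 15 | 6.3% | 12.5% | 3510 | 0.43 | 0.85 |
| 30 | 0 | 0% | 12.5% | 3420 | 0 | 0.88 |

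The combined 12.5% has a 95% interval of ±1.96 × √(0.125 × 0.875 / 240) = ±4.2 points, or 8.3% to 16.7%.

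Dropping stoppers from the denominator does not cure the problem: with 15 direct stops, 15 / (240 − 15) = 6.7% instead of 6.3%, still against 12.5%.

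**The case against.** The strongest reply is that the study does not lose sight of stoppers. Permanent stops before month 6 lower the primary proportion, and reasons for discontinuation and the related adverse events are tabulated. This stands. A reader might infer that the worst tolerability outcomes are missed by the study as a whole; the documents do not support that. The gap is confined to items 2 and 3, and to short suspensions that the proportion-at-target endpoints cannot see.

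Three other stronger readings also go too far.
- That the SAP scores a stopper as having had no down-titration. It states no scoring rule. This is an inference from the wording, although the likely one.
- That Protocol 6.5 makes the down-titration rate the single measure of tolerability. It calls it an indication, and names achieving and maintaining 97/103 mg as the outcome for the primary objective. Describing titration patterns is also an aim in its own right, so a down-titration-only count has a legitimate place.
- That the endpoints fail because they cannot be set beside the titration trial summarised in Protocol 1.1, where success meant patients "achieved the target LCZ696 97 mg sacubitril / 103 mg valsartan bid dose and had no down-titration or dose interruption". That wording does show the two events treated together. But the trial figure covers 12 weeks and excludes discontinuations unrelated to adverse events, and the documents never propose comparing items 2 or 3 with it.

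It is also fair that early exit shortens person-time and so raises the rate. In the illustration the offset is slight: 15 events give 0.43 per 100 person-months over 3510 person-months, against 0.42 over 3600.

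**Conclusion.** The point holds for these two secondary endpoints. As worded, they can understate intolerance of 97/103 mg, and they fall when stopping replaces stepping down. The primary endpoint is not affected.

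The amount cannot be estimated from the documents, which give no split between stepping down, suspending and stopping; no fixed factor of understatement is supported. The range of 12.5% to 0% for the same 30 patients shows how far the measure could move and is not a forecast. It treats the difference between two planning percentages, taken from different settings and times, as patients leaving the dose. It also ignores late arrivals at the dose and patients who return to it.

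**What to change.** In SAP 2.7.1 and 2.7.2:
- Define down-titration, and set the item 2 denominator as all patients who reached 97/103 mg.
- Keep the down-titration-only proportion and count.
- Beside them, report temporary suspensions and permanent stops made directly from 97/103 mg, with the recorded reason where available.
- Add the proportion with a first move off 97/103 mg by any of the three routes, with its 95% confidence interval.
- Keep permanent stops out of the Poisson count, because they cannot recur, and report them as a separate component.

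While these sections are open, two related items need reconciling. SAP 2.1.1 defines the event for the incidence density rate as reaching 200 mg, whereas 2.7.2 uses dose reductions. The sample Poisson code in 5.4.2 shows no person-time offset.

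The cost is a SAP revision and one extra derived variable. The data are already collected in the Dosage Administration Record, the action-taken field for adverse events and the study discontinuation page. The Dosage Administration Record is not described as holding reasons for dose changes, so these may have to come from the other two sources and will sometimes be missing. The reported rate may become less favourable. No treatment rule changes.

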2.7.2 Statistical hypothesis, model, and method of analysis

The data analysis will be primarily descriptive. For the secondary efficacy outcomes, the proportion of patients on LCZ696 97 mg sacubitril / 103 mg valsartan bid at 12 months, the proportion of patients requiring down titration, and the proportion of patients treated in accordance to guideline recommended doses of beta blockers and MRAs will be presented along with the 95% Confidence Intervals using binomial proportion to assess the precision.

Novartis	For business use only	Page 14
SAP		PARASAIL / LCZ696BCA02

The number of down titrations during the 12 month treatment periods will be described with a Poisson distribution and the incidence density rate (IDR) as the number of dose reductions per 100 person – month of follow up.

The change in the Six Minute Walk Test from baseline to 6 and 12 months of treatment will be assessed along with the 95% confidence intervals using Student's t-test for paired observations.

The time to LCZ696 up-titration to 97 mg sacubitril / 103 mg valsartan bid and the duration on treatment for each dose will be assessed with the Kaplan Meier estimator of the survival function.

Duration of treatment on each dose of LCZ696 will be summarized descriptively.

2.7.3 Handling of missing values/censoring/discontinuations

There will be no replacement or imputation of missing values. All analysis will be conducted on observed cases only. For patients lost to follow up after achieving the LCZ696 dose of 97 mg sacubitril / 103 mg valsartan bid, the conservative approach will be used according to which they will be considered as not staying on treatment.

A sensitivity analysis could be conducted for the PPS as required.

2.8 Safety analyses

2.8.1 Adverse events (AEs)

Adverse events (AEs) will be classified according to the latest MedDRA dictionary of terms and summarized using :

- The total number of AEs
- The total number and percentage of patients who experience an AE overall,
- The number and percent of patients who experience an AE within each system organ class (SOC) and preferred terms (PTs) within individual SOCs.

Analysis of the number of patients who experience each AE will be performed in the following manner: patients experiencing the same AE multiple times will only be counted once for the corresponding PT; similarly, if a patient experiences multiple AEs within the same SOC, that patient will be counted only once for that SOC.

Number and percent of patients who experience an SAE within each system organ class (SOC) and preferred terms (PTs) within individual SOCs will also be summarized.

AEs and SAEs with related to the study treatment (definitely related, probably related, possibly related) will be summarized.

Summary of the total number of AEs by seriousness (serious, non-serious), severity (mild, moderate, severe), relationship to study medication (definitely related, probably related, possibly related, unlikely related, definitely not related), action taken and outcome will also be provided.

Any AE/SAE occurred during the study will be included in AE/SAE summary tables, i.e. AEs/SAEs occurred on or after study day 1 and up to 30 days after the discontinuation of the study drug.

The following summaries will be generated for AEs:

- All adverse events
- Serious adverse events
- Adverse event by severity grade
- Adverse events causing study drug discontinuation
- Adverse events requiring dose adjustment or study-drug interruption
- Investigator reported causes of deaths by primary system organ class and preferred Term

The above information also be listed. Analysis will be based on SAF.

2.8.1.1 Adverse events of special interest / grouping of AEs

Liver events of special interest (AESI) which consist of LFTs elevations will be presented. Adverse event (liver events) of special events defiend as:

- Any clinical event of jaundice (or equivalent term)
- ALT or $AST > 3 \times ULN$ (accompanied by general malaise, fatigue, abdominal pain, nausea, or vomiting, or rash with eosinophilia)
- Any event with a preferred term (PT) in the MedDRA dictionary falling under the SMQ sub-module "Drug-related"
 - hepatic failure, fibrosis and cirrhosis, and other liver damage-related conditions;
 - o non-infectious hepatitis;
 - benign, malignant and unspecified liver neoplasms
 - Hy's law case (PT)

2.8.2 Deaths

Primary cause of death will be summarized by system organ class (SOC) and preferred term (PT) by providing number and percent. Death information will be summarized on SAF.

2.8.3 Laboratory data

The Laboratory Analysis will be carried out on SAF.

Clinically notable laboratory findings are defined as in section 5.3.

The summary of laboratory evaluations will be presented for laboratory tests: hematology which include hemoglobin, hematocrit, RBC count, WBC count, platelet count, and blood chemistry which includes blood urea nitrogen (BUN), creatinine, AST (SGOT), ALT (SGPT), alkaline phosphatase, potassium, eGFR, chloride, and uric acid as conduct per routine care.

Descriptive summary statistics (mean, median, standard deviation, min and max) for the change from baseline to each study visit will be presented. These descriptive summaries will be presented by laboratory test. Change from baseline will only be summarized for subjects with both baseline and post baseline values and will be calculated as defined in $\underline{\text{section } 2.1.1}$ i.e. General definations.

In addition, shift tables will be provided for all parameters to compare a subject's baseline laboratory evaluation relative to the visit's observed value. For the shift tables, the normal laboratory ranges will be used to evaluate whether a particular laboratory test value was normal, low, or high for each visit value relative to whether or not the baseline value was normal, low, or high. These summaries will be presented by laboratory test.

The number and percentage of subjects with clinically notable laboratory results after baseline will be presented. Clinically notable laboratory results, for those parameters where ranges are available, are given in Table 1 below. For the calculation the denominator are based on the evaluable post-baseline subjects who did not have the notable abnormality at baseline.

For all laboratory evaluation scheduled and unscheduled laboratory measurements will be taken into account.

As confirmed from the sites about erroneous lab unit entry of the parameters creatinine and uric acid, the appropriate conversion of these units will be handled programmatically.

Parameter	Original unit	Standard unit	Conversion factor
Creatinine	mmol/l	umol/L	1000
Creatinine	Mg/dL	umol/L	88.40
Urate	mmol/L	umol/L	1000

The parameters that will be considered for unit conversion are Creatinine and Uric acid.

Table 1 Clinical notable criteria for selected laboratory tests

Hematology	
RBC count	>50% increase, >20% decrease
Hemoglobin	>50% increase, >20% decrease
Hematocrit	>50% increase, >20% decrease
WBC count	>50% increase, >50% decrease
Platelet count	>75% increase, >50% decrease
Blood Chemistry	
ALT (SGOT)	>150% increase
AST (SGPT)	>150% increase
BUN	>50% increase
	>14.28 mmol/L
Creatinine	>50% increase
	>136.8 µmol/L
СРК	>300% increase
Alkaline phosphatase	>100% increase
Potassium	>20% increase, >20% decrease
	$\geq 6.0 \text{ mmol/L}$
	>5.0 mmol/L
	<3.5 mmol/L
Chloride	>10% increase, >10% decrease

...

Uric acid

>50% increase

In the above table increase and decrease are defined as compared to the baseline value.

2.8.3.1 Urinalysis

Not Applicable.

2.8.4 Other safety data

2.8.4.1 ECG and cardiac imaging data

Electrocardiograms will be conducted as per routine care and documented in the site's source documents. No analysis will be performed.

